4. OBJECTIVES

[figure not shown]
To evaluate safety and anti-tumoral effect of FLX475 combined with pembrolizumab in subjects with advanced or metastatic gastric cancer. The primary and secondary efficacies will be evaluated by RECIST 1.1 and iRECIST.

4.1. Primary Objectives

- To assess the anti-tumor efficacy of FLX475 in combination with pembrolizumab in subjects with advanced or metastatic gastric cancer by Objective Response Rate (ORR) by RECIST 1.1

4.2. Secondary Objectives

- To assess of the clinical efficacy including DCR (complete response + partial response + stable response), TTR, DoR, and PFS by RECIST 1.1
- To assess OS
- To assess of the clinical efficacy by iRECIST including iORR, iDCR, iTTR, iDoR, iPFS
- To assess the safety and tolerability of FLX475 combined with pembrolizumab based on Laboratory assessments and AE, SAE using NCI-CTCAE v 5.0

5. STUDY DESIGN

5.1. Overall Design and Plan

This clinical study is a Phase 2, open-label study to assess the efficacy, safety profile of FLX475 combined with pembrolizumab in patients with advanced or metastatic gastric cancer. Approximately 90 subjects may be enrolled across two cohorts to examine the safety and efficacy. This study is designed to assess the potential anti-tumor activity when administered at the 100mg QD of FLX475 with pembrolizumab and will be conducted (2) cohorts as detailed below.

Cohort 1: Checkpoint inhibitor naïve Epstein-Barr Virus (EBV) negative gastric cancer subjects who have progressed on at least 2 prior systemic treatments for advanced or metastatic gastric cancer

Cohort 2: Checkpoint inhibitor naïve Epstein-Barr Virus (EBV) positive gastric cancer subjects who had at least 1 prior systemic treatment for advanced or metastatic gastric cancer

Cohort 1 will be enrolled in two stages, starting with at least 10 subjects in the first stage. Expansion to the stage 2 of cohort 1 will be based on the overall safety and efficacy data as well as any available PK and PD data when the 10th subject completes 4 cycles (or 12 weeks; after 2nd response assessment) or withdrawn from the study, whichever occurs first. During this data review, Sponsor can determine study discontinuation if there is no responder from 10 subjects in the first stage. Once expanded, 20 additional subjects will be accrued in stage 2 and further assessment for the safety and efficacy based on the accumulated data up to 30 subjects (10 from stage 1 and 20 stage 2) will be performed. Referring to the published data[11], 15% of ORR is the minimum criteria to proceed for the next stage in the study. If the posterior probability for the ORR $\geq 15\%$ is less than 80%, the enrollment to the cohort will be paused and assessed overall safety along with PK and PD data available. In consideration of the cumulative overall safety and efficacy up to the 30 subjects along with the other competitive landscape, the cohort 1 could be expanded further up to 60 subjects at maximum including the previous subjects enrolled or could be stopped for further enrollment. Also, if required, there could be another stage to investigate further after 2nd stage as well.

Cohort 2 will be enrolled in similar way to the cohort 1 starting with 10 subjects in the first stage and expanded to the second stage based on the overall safety and efficacy as well as available PK and PD data when the 10th subject completes 4 cycles (or 12 weeks; after 2nd response assessment) or withdrawn from the study, whichever occurs first. During this data review, Sponsor can determine study discontinuation if there is no responder from 10 subjects in the first stage same as cohort 1. Referring to the published data[12], for cohort 2 30% of ORR is the minimum criteria to proceed for the next stage in the study. Once determined to the second stage, additional 10 subjects will be enrolled for cohort 2 and If the posterior probability for the ORR $\geq 30\%$ is less than 80%, the enrollment to the cohort will be paused and assess overall safety along with PK and PD data available. If required, further enrollment up to 30 in total as maximum might be performed based on the overall data up to 20 subjects in comparison with the competitive landscape. Also, if required, there could be another stage to investigate further after 2nd stage as well.

The next stage of each cohort will be determined after the comprehensive evaluation from the previous stage by the Independent Data Monitoring Committee(IDMC).

To study potential PD biomarker changes that may be indicative of combined pathway inhibition by the pembrolizumab and FLX475 combination, paired (pre- and post-treatment) tumor biopsies will be obtained from all subjects.

The screening period (Day -30 to Day -1) lasts up to approximately 30 days prior to Cycle 1 Day 1. Patients must meet all Inclusion/Exclusion Criteria to participate in the study. All screened patients will provide written Informed Consent prior to any study procedures.

Once screening procedures are completed and eligibility is confirmed, subjects will start treatment Cycle 1 with FLX475 and pembrolizumab on Day 1. Subject will continue to receive study treatment for a maximum of 35 cycles (approximately 2 years) or until subject withdrawal from the study, confirmed progression of cancer, intolerable study treatment-related toxicity despite appropriate dose modification and supportive treatment, pregnancy or breastfeeding, substantial noncompliance with study procedures, loss to follow-up, or study termination by the Sponsor, whichever occurs first.

For subjects who have radiological Progressive Disease (PD) by Response Evaluation Criteria in Solid Tumor (RECIST) 1.1 as determined by the investigator will decide whether the subject can continue to receive study treatment until repeat, confirmatory imaging is obtained using modified RECIST for immunotherapies (iRECIST) for subject management.

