7.4. Discontinuation of Study Treatment

Discontinuation of study treatment does not represent withdrawal from the study.

The investigator may discontinue treating a subject with study treatment or withdraw the subject from the study at any time for safety or administrative reasons. The subject may decide to discontinue study treatment or withdraw from the study at any time for any reason.

FLX475 treatment must be discontinued but the subject should continue to be monitored in the study for any of the following reasons:

- Any study intervention-related toxicity specified as a reason for permanent discontinuation as defined in the guidelines for dose modification due to AEs in Section [7.3.1](#).

Pembrolizumab treatment must be discontinued but the subject should continue to be monitored in the study for any of the following reasons:

- Completion of 35 treatments (approximately 2 years) with pembrolizumab
- Any study intervention-related toxicity specified as a reason for permanent discontinuation as defined in the guidelines for dose modification due to AEs in Section [7.3.2](#).

Discontinuation of treatment may be considered for subjects who have attained a confirmed complete response (CR) and have been treated for at least 8 cycles (at least 24 weeks), receiving [2 cycles of the combination including 2 doses of pembrolizumab and at least 80% of the planned doses of FLX475] beyond the date when the initial CR was declared.

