8.3. End of Treatment Period

A subject may elect to discontinue treatment or withdraw consent from the study at any time for any reason. This will mean that no further information may be collected for the purpose of the study. Furthermore, it may mean that further subject follow-up on safety cannot occur. If a subject wants to withdraw consent, the investigator should explain the difference between treatment withdrawal and withdrawal of consent for study participation and explain the options for continued follow up after withdrawal. If the subject's agrees to further follow up, the subject will undergo the procedures for the EOT visit and follow up as outlined in the Schedule of Procedures/Assessments (Table [1.2:1](#)).

Unless subjects withdraw consent or are lost to follow-up, all subjects who discontinue study treatment prior to Progressive Disease (PD) will undergo tumor imaging at the time of treatment discontinuation (\pm 4-week window). If previous tumor imaging was obtained within 4 weeks prior to the date of discontinuation, then imaging at treatment discontinuation is not mandatory.

Subject will be asked to return all unused study drug and packaging at the end of the study or at the time of study drug discontinuation.

The investigator will promptly explain to the subject involved that study treatment and procedures will be discontinued for that subject, and appropriate medical treatment and other necessary measures will be provided.

Subjects who consent to follow-up will be monitored for disease progression and/or survival.

Study disposition information will be collected on the appropriate eCRF. Subjects who withdraw early from the study will be discontinued for 1 of these primary reasons: AE(s), lost to follow-up, progression of disease, withdrawal of consent, pregnancy, study terminated by Sponsor, or other.

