9.1.2.2. During Treatment

All images during treatment will be sent to central imaging for further analysis. The first imaging assessment during study treatment should be performed 6 weeks (± 7 days) from Cycle 1, Day 1.

Subsequent tumor imaging should be performed every 6 weeks (± 7 days) or more frequently if clinically indicated for the first year of treatment. After 1 year, subjects who continue to receive study treatment will have imaging performed every 9 weeks (± 7 days) for up to 1 additional year.

The timing of tumor imaging should follow calendar days and should not be adjusted for delays in cycle starts. Tumor imaging should continue to be performed until Progressive Disease (PD) is identified by the investigator (unless the investigator elects to continue treatment and follow iRECIST), the start of new anticancer therapy, withdrawal of consent, loss to follow-up, death, 2 years of study treatment, or termination of the study by the Sponsor, whichever occurs first.

Objective response should be confirmed by a repeat imaging assessment. Tumor imaging to confirm PR or CR should be performed at least 4 weeks after the first indication of a response is observed. Subjects will then return to regularly scheduled imaging, starting with the next scheduled imaging time point. Subjects who receive additional imaging for confirmation do not need to undergo the next scheduled tumor imaging if it is less than 4 weeks later; tumor imaging may resume at the subsequent scheduled imaging time point.

Per iRECIST, investigator-assessed Progressive Disease (PD) in the clinically stable subjects should be confirmed by the investigator 4 to 8 weeks after the first radiologic evidence of Progressive Disease (PD). A subject with unconfirmed Progressive Disease may continue to receive study treatment at the discretion of the investigator until progression is confirmed by the investigator, provided the subject has met the conditions detailed in Section 9.1.3. Subjects who have confirmatory imaging do not need to undergo the next scheduled tumor imaging assessment if it is less than 4 weeks later; tumor imaging may resume at the subsequent scheduled imaging time point, if clinically stable.

Subjects who have confirmed Progressive Disease (PD) by iRECIST, as assessed by the investigator, will discontinue study treatment. Exceptions are detailed in Section 9.1.3.

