11.4.2. Efficacy Analysis

Efficacy analysis will be conducted based on Treated Set and Tumor Evaluable Set. Tumor-related endpoints will be analyzed based on investigator's assessment using RECIST version 1.1, and the result from assessment using iRECIST also be presented.

The primary efficacy endpoint is Objective Response Rate (ORR) defined as the proportion of subjects whose confirmed best overall response is either Complete Response (CR) or Partial Response (PR) according to RECIST version 1.1. The best overall response is the best response recorded from the treatment start date until the earliest of disease progression or last evaluable tumor assessment before events such as start of new anticancer therapy, death, lost to follow-up, etc.

The DCR is defined as the proportion of subjects with confirmed best overall response of CR, PR or SD according to RECIST version 1.1.

The ORR and DCR will be presented with exact 95% Confidence Interval (CI) using the Clopper-Pearson method. Based on the cumulative data about ORR along with prior assumption at each stage, posterior probability of ORR $\geq 15\%$ for cohort 1 and ORR $\geq 30\%$ for cohort 2 would be computed to determine go/no-go decision of the next stage. This cumulative data analysis will be implemented only if at least one response is observed from stage 1 of each cohort.

Time-to-event endpoints, including TTR, DoR, PFS and OS, will be summarized descriptively and graphically using Kaplan-Meier (KM) methodology. Median KM estimates and 95% CI will be presented. For the tumor-related time-to-event endpoints, subjects who have not experience any event (Progressive Disease (PD) or Death) at the time of analysis will be censored at the date of the last evaluable tumor assessment. However, if the subject progresses or dies after two or more consecutive missed assessments or start of new anticancer therapy, the subject will be censored at the time of the last evaluable assessment prior to starting new anti-cancer therapy/missed assessments. If the subject has no evaluable baseline/post-baseline assessment, subject will be censored at the date of first administration of study treatment.

TTR is defined as the time from the date of first administration of study treatment to first documented CR or PR.

DoR is measured from the date of the first observation of tumor response (CR or PR, whichever occurs first) to the date of disease progression or death for the subject with an objected response.

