11.5. Interim Analysis

The study is planned initially for 2-stage design for both cohorts but there might be more than 2 stages depending on the results for each cohort. Based on the initial plan with 2-stage design, the interim analysis for each cohort will be performed when the initial 10 subjects of each cohort completes 4 cycles (or 12

weeks; after 2nd response assessment) or withdrawn from the study, whichever occurs first. At this time both efficacy and safety results as well as any available PK and PD data will be reviewed by the IDMC. The number of subjects for the next stage will be determined based on the interim data analysis as well. Study discontinuation due to futility may be recommended by the IDMC to the Sponsor. More details about the decision making based on the interim analysis will be described in charter.

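### The plan has two triggers for the stage-1 review, and one lets the 10th subject's early withdrawal from the study set the data cut before others have had their second scan

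*Protocol*

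**What the plan says.** **Single-subject trigger.** Protocol 5.1 times the decision on stage 2 to "when the 10th subject completes 4 cycles (or 12 weeks; after 2nd response assessment) or withdrawn from the study, whichever occurs first". The same words appear there for both cohorts, and again in the Synopsis and SAP 2.1.

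**All-ten trigger.** Protocol 11.5 says "the interim analysis for each cohort will be performed when the initial 10 subjects of each cohort completes 4 cycles", followed by the same 12-week and withdrawal alternatives. SAP 16.1 repeats this. Protocol 11.4 refers the reader to 11.5 for the interim analysis. I find no equivalent pointer in the SAP, so SAP 2.1 and SAP 16.1 stand side by side.

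**What depends on the cut.** Protocol 5.1 states that "Sponsor can determine study discontinuation if there is no responder from 10 subjects in the first stage", and applies this to cohort 2 as well. Under Protocol 11.4.2 and SAP 12.1, the posterior probability informs go/no-go for the next stage and is computed only if stage 1 shows at least one response.

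**Imaging.** "The first imaging assessment during study treatment should be performed 6 weeks (± 7 days) from Cycle 1, Day 1"; later scans follow every 6 weeks (±7 days) in the first year. The second assessment therefore falls at about week 12.

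**Withdrawal.** Protocol 7.4 states: "Discontinuation of study treatment does not represent withdrawal from the study".

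**The concern.** The stage-1 review is meant to follow the second response assessment. If the 10th subject reaches week 12, the two triggers give the same date, because the earlier subjects are then further along or have left. If the 10th subject withdraws from the study early, the 5.1 wording is met at once. Subjects enrolled shortly before may then have had one scan or none, whereas 11.5 would wait for them.

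A response that has not yet been seen can matter in two ways. It can leave the count at zero, which opens the discontinuation option and also removes the posterior calculation. It can also keep the posterior below 80%. The trial is open-label, so an ambiguous cut date leaves room to choose the date after responses are known.

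**Working it through.** **1. The plan's own figures reproduce.** With a uniform prior the posterior is Beta(1+X, 1+N−X).
- Cohort 1, 7 of 30: P(ORR ≥ 15%) = 0.918 (plan: 92%).
- Cohort 2, 8 of 20: P(ORR ≥ 30%) = 0.852 (plan: 85%).

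These do not depend on the trigger. They confirm the model used in step 4.

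**2. How many subjects could be short of week 12.** Let the 10th subject withdraw at week w, with a constant gap of a weeks between enrolments. The subject enrolled j places earlier is then at week w + j·a, and is short if w + j·a < 12 (j = 1 to 9). The documents give no accrual rate, so a is an assumption and is varied. The counts are upper limits, because anyone who had already left would drop out of them.

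| Gap (weeks) | Withdrawal at week 1 | Week 3 | Week 6 |
|---|---|---|---|
| 0.5 | 9 | 9 | 9 |
| 1 | 9 | 8 | 5 |
| 2 | 5 | 4 | 2 |
| 3 | 3 | 2 | 1 |
| 4 | 2 | 2 | 1 |
| 6 | 1 | 1 | 0 |
| 9 | 1 | 0 | 0 |
| 12 | 0 | 0 | 0 |

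**3. Chance that no responder has been seen.** Assumptions: one enrolment every 15 days (2.14 weeks); the 10th subject withdraws from the study at week 3 as a non-responder; half of responses first appear at each of the two scans; a response counts when first seen. Here p is the true ORR.

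Subjects 9, 8, 7, 6 and 5 are at weeks 5.1, 7.3, 9.4, 11.6 and 13.7. With scans exactly at weeks 6 and 12, subjects 1–5 have had both, 6–8 have had one, and 9 has had none.

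- 11.5 rule: (1−p)^9
- 5.1 rule, scans on the nominal day: (1−p)^5 × (1−p/2)^3
- 5.1 rule, subjects 6 and 9 scanned early within ±7 days: (1−p)^6 × (1−p/2)^3

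| True ORR | 11.5 rule | 5.1, early scans | 5.1, nominal scans |
|---|---|---|---|
| 15% | 0.85^9 = 0.232 | 0.85^6 × 0.925^3 = 0.30 | 0.85^5 × 0.925^3 = 0.351 |
| 30% | 0.70^9 = 0.040 | 0.70^6 × 0.85^3 = 0.07 | 0.70^5 × 0.85^3 = 0.103 |

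**4. What one unseen response can do to the posterior at N = 10.**
- Cohort 1, ORR ≥ 15%: 2 of 10 gives 0.779; 3 of 10 gives 0.931.
- Cohort 2, ORR ≥ 30%: 4 of 10 gives 0.790; 5 of 10 gives 0.922.

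In each cohort a single response separates a value below 80% from one above it.

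**The case against.** **Precedence is partly stated.** Protocol 11.4 sends the interim analysis to 11.5, so a careful reader would probably apply the all-ten rule. This stands and lowers the risk. It does not withdraw the wording in the Synopsis and 5.1, and it does not resolve the SAP. The charter named in 11.5 is to give details of decision making; it is not available here.

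**The 10th subject might mean the tenth to reach the milestone.** That reading would make the two rules agree, but the plain sense is the tenth enrolled.

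**The stop is discretionary.** The sponsor may stop; it is not obliged to. The IDMC makes a comprehensive evaluation before the next stage. Neither document says that the review takes place on the day of withdrawal, or that subjects with pending scans count as non-responders. This stands. The calculation needs only that their later responses have not yet been seen.

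**The probabilities rest on assumed inputs.** This also stands. They are conditional on the 10th subject withdrawing early, and nothing in the documents gives the chance of that. Response in this trial must also be confirmed: "Tumor imaging to confirm PR or CR should be performed at least 4 weeks after the first indication of a response is observed". A response first seen at week 12 is therefore unconfirmed at the cut under either rule.

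**Stronger readings that the documents do not support:**
- A reader might infer that stopping treatment for progression, for instance at the week-6 scan, fires the trigger. Protocol 8.3 invites this: "Subjects who withdraw early from the study will be discontinued for 1 of these primary reasons: AE(s), lost to follow-up, progression of disease". But 7.4 separates stopping treatment from leaving the study, and such subjects enter follow-up. The scenario is too doubtful to rely on.
- A reader might infer that the two cohorts could be cut under different rules. Both carry the same wording in 5.1, and 11.5 covers each cohort.
- A reader might infer that any drop-out among the ten advances the review. Only the 10th subject's withdrawal does.

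**Conclusion.** The inconsistency is real and lies within each document: Synopsis and Protocol 5.1 against 11.5, and SAP 2.1 against 16.1. It has an effect only when the 10th subject withdraws from the study before week 12 and accrual is fast enough that earlier subjects are still short of their second assessment. The 5.1 wording then permits a review on incomplete response data, which raises the chance of seeing no responder.

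The size cannot be fixed from the documents. For a week-3 withdrawal, anywhere from all nine of the others to none are affected, depending on accrual. Under the step 3 assumptions, the chance of seeing no responder is higher by about 0.07 to 0.12 at a true ORR of 15%, and by about 0.03 to 0.06 at 30%. These figures illustrate the direction and rough scale; they do not show that the review is biased in general. The point merits correction because the remedy is nearly free.

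**What to change.** In the Synopsis, Protocol 5.1 and SAP 2.1, for both cohorts, replace the 10th-subject trigger with the rule already in Protocol 11.5 and SAP 16.1. Suggested wording: the stage-1 cut is taken when each of the initial 10 subjects has completed 4 cycles (or 12 weeks, after the second response assessment) or has withdrawn from the study, including death and loss to follow-up; one subject's withdrawal does not bring the cut forward for the others.

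Naming death and loss to follow-up keeps one lost subject from leaving the condition unmet. Add the same clarification to 11.5 and 16.1 so that all sections match.

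The cost is wording only; sample sizes, thresholds and treatment are unchanged. When the 10th subject withdraws early, the review waits under 12 weeks for the remaining second scans. In the step 3 example, subject 9 is at week 5.1, so the wait is about 12 − 5.1 = 6.9 weeks.

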5.2. End of Study and Length of Study

The end of study is defined as the date when the last subject, last visit (LSLV) occurs or the date at which all required follow-up data and documentation have been received by Sponsor, whichever occurs later. The study is expected to be performed for about 2 years from End of Treatment visit of last subject and the duration may be shorten or extended depending on the study conditions.

